10.3 STUDY ASSESSMENTS AND PROCEDURES

Patients likely to fulfill the inclusion criteria and not meet any exclusion criteria will be provided with information on the study and invited to attend a subsequent screening visit. Only patients who have signed the informed consent form will participate in any study related procedures including blood testing and ECG.

At screening visit (Assessment 1) subjects will have a physical examination and an EDSS score rated. Blood samples will be taken for renal and liver function and a baseline ECG performed. Patients will complete a nine-hole peg test and a JTT. T25FW will be recorded and the patients invited to complete the MSIS-29, MSWS-12, DASH, AMSQ and SF-36 questionnaires. Patients with any abnormalities on ECG, blood tests will not be invited to a baseline visit and considered a screening failure.

Following screening visit subjects fulfilling the inclusion / exclusion criteria will have two baseline visits (Assessments 2 and 3) at the end of week one and end of week two. The 9-HPT, JTT and T25FW will be repeated to allow for training effects. Patients will be randomised to group A or group B and receive study medication or placebo at baseline visit based on their blinded randomisation (Assessment 3).

The first treatment period will be from the start of week 3 until the end of week 10. Patients will have an assessment at the end of week 6 (Assessment 4) and the end of week 10 (Assessment 5). At both assessments patients will have the 9-HPT, JTT, T25FW, MSIs-29, MSWS-12, DASH, AMSQ and SF-36 recorded. Weeks 11 and 12 will be a washout period (no drug/placebo). Assessment 6 will occur at the end of week 12 and will include recording of 9-HPT, JTT, T25FW, MSIs-29, MSWS-12, DASH, AMSQ and SF-36. Any adverse events will be recorded at each visit as will the use of concomitant medications.

The second treatment period will begin at the start of week thirteen with groups A and B switching study drug / placebo in a blinded manner. The second treatment period will continue for a further 8 weeks with two more assessments at week 16 (Assessment 7) and week 20 (Assessment 8). At both of these assessments subjects will complete the 9-HPT, JTT, T25FW, MSIs-29, MSWS-12, DASH, AMSQ and SF-36. At the end of week 20 and EDSS score will be recorded. Any adverse events will be recorded at each visit as will the use of concomitant medications.

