There will be a final washout period (weeks 21 and 22) after which a final visit (assessment 9) will occur and subjects once again completing 9-HPT, JTT, T25FW, MSIs-29, MSWS-12, DASH, AMSQ and SF-36 and having an EDSS score recorded. Once again adverse events will be recorded.

(See Schedule of Events, page 15)

Figure 2: Schedule of events

Assessment	1 Screening Visit	2 Baseline Visit	3 Base - line Visit	4 Rx Phase 1	5 End of Rx Phase 1	6 End Wash- out phase	7 Rx Phase 2	8 End of Rx Phase 2	9 End of 2 week washout
Time (start/end week)	week 1 (start)	week 1 (end)	week 2 (end)	week 6 (end)	week 10 (end)	week 12 (end)	week 16 (end)	week 20 (end)	week 22 (end of trial)
Informed consent	X								
Serum pregnancy test (female subjects)	X								
EDSS	x							X	X
ECG	X								
Receiving Medication	No	No	Start drug	Continu e drug	Stop drug	Start drug	Continu e drug	Stop drug	Wash out
9- HPT	x	x	x	x	x	x	x	x	X
JTT	x	x	x	x	x	x	x	x	X
T25FW	x	x	x	x	x	x	x	x	X
MSIS-29	x		x	x	x	x	x	x	X
MSWS-12	x		x	x	x	x	x	x	X
DASH	x		x	x	x	x	x	x	X
AMSQ	x		x	x	x	x	x	x	x
SF-36	X		X	X	X	X	X	X	X
Adverse event recording				X	X	X	X	X	X
Concomitant medication recording	X		X	X	X	X	X	X	X
Study Drugs dispensed			X			X			

Description of Study Assessments

Medical and Surgical History will be recorded with particular attention on the diagnosis of MS, duration of MS and MS subtype.

Demographics

The date of birth, gender and race will be recorded.

Physical Examination

The complete physical examination will include the evaluation of the neurological system and a recording of the EDSS score and T25FW.

ECG Test

One ECG including a 12-lead examination will be performed at Screening (assessment 1).

Abnormal findings will be noted for clinical significance. The report will be signed by the investigator.

Clinical Laboratory Tests

1. Haematology: haemoglobin, WBC, RBC, platelet count
2. Biochemistry: creatinine or creatinine-clearance, sodium, potassium, liver function tests
3. All laboratory results will be reviewed and the reports signed by the investigator who will record in the CRF whether they are normal, abnormal but not clinically significant, or abnormal and clinically significant.

Pregnancy Tests

Serum pregnancy test and urine pregnancy test in women of childbearing potential will be performed.

Concomitant Medication

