13.5 EFFICACY ANALYSIS

Primary efficacy endpoint:

An upper limb responder to fampridine will be defined as a patient with both of the two "on treatment" 9-HPT assessments (assessments 4 & 5 or 7 & 8) improving 20% from the average of the baseline assessments (1, 2 & 3).

Secondary efficacy endpoints:

- a) A secondary measure of upper limb responsiveness will be defined as a 20% improvement in from baseline in the average time taken to complete all seven tasks on the JTT “on treatment” (assessments 4 & 5 or 7 & 8) compared with baseline assessments (assessments 1,2 & 3).
- b) A mobility responder to dalfampridine will be defined as a patient with both of the two “on treatment” T25FW assessments (assessments 4 & 5 or 7 & 8) being better than the maximum of any of the four “off treatment” assessments (assessments 1, 2, 3, & 9). Otherwise the patient will be deemed a non-responder.
- c) The responders to the 9-HPT and/or JTT will be compared to the non-responders in relation to their changes in the DASH and AMSQ on treatment and off treatment at the baseline assessment. The change in the DASH and AMSQ in responders at Assessment 5 or 8 (week 10 or 20) will be compared to non-responders at that time-point.

Upper limb response will be examined at the end of treatment phase 1 and repeated at the end of the trial by comparing patients receiving active drug with those receiving placebo to assess any placebo effect and allow assessment of any residual beneficial effect on those who receive fampridine in treatment phase 1 and then switch to placebo in treatment phase 2. Response will again be considered as a 20% improvement in the 9HPT in the active treatment group compared with placebo and a 20% improvement from baseline in the time taken to complete all seven tasks in the JTT. See earlier comment

- d) The responders to the T25FW will be compared to the non-responders in relation to their changes in the MSWS-12 on treatment and off treatment at the baseline assessment. The change in the MSWS-12 in responders at Assessment 5 or 8 (week 10 or 20) will be compared to non-responders at that time-point.

The patients’ scores on the MSIS-29 (physical) and SF-36 will be examined in relation to the objective changes (responder/non-responder) in the 9-HPT, JTT and the T25FW.

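### The second active-v-placebo comparison, meant to show a residual fampridine effect, has no clearly named visit and does not isolate that effect alone, while the week 12 washout visit goes unused

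*Combined protocol and SAP*

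**What the plan says.** Section 13.5, with the same text in 9.4 and 10.3.2, examines upper limb response at the end of treatment phase 1. The examination is then "repeated at the end of the trial by comparing patients receiving active drug with those receiving placebo to assess any placebo effect". The same sentence gives it a second purpose, to assess "any residual beneficial effect on those who receive fampridine in treatment phase 1 and then switch to placebo in treatment phase 2".

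Figure 2 in section 10.3 heads the Assessment 9 column "week 22 (end of trial". Sections 10.4 and 13.8 also tie the end of the trial to the last visit. Section 10.3 describes that visit: "There will be a final washout period (weeks 21 and 22) after which a final visit (assessment 9) will occur".

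For the washout between the phases, section 10.3 states: "Assessment 6 will occur at the end of week 12 and will include recording of 9-HPT, JTT, T25FW". Treatment phase 2 begins at the start of week 13.

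The stated analyses do not use that visit. The 9-HPT and JTT responses take Assessments 1 to 3 as baseline, and the T25FW off-treatment set is Assessments 1, 2, 3 and 9. Section 13.1 names one test, a Wilcoxon signed rank test on paired on-treatment measures. No period, sequence or carryover analysis is described.

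**The concern.** Three things need attention.

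- **Timing.** Read by the schedule's label, the second comparison falls at week 22, when nobody is receiving active drug or placebo. Read by its own wording, it falls in treatment phase 2.
- **What the phase 2 comparison measures.** Group A is fampridine then placebo and group B the reverse (section 10.3.3). All phase 2 placebo patients are therefore in group A. Any lasting benefit raises their placebo-period result and narrows the contrast, which looks like a weaker drug.
- **Unused data.** At week 12 both randomised groups are off treatment and have been measured on the 9-HPT and JTT, but no analysis compares them.

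The trial relies on paired on-treatment results. If fampridine has a lasting effect, the within-patient difference pooled over the two sequences is too small, and the reader needs some estimate of by how much.

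**Working it through.** **Inputs.** From the documents: 80 patients, 40 per sequence (13.2); significance level 0.05 (13.7), taken as two-sided because sidedness is not stated; about 30% responding on fampridine (13.2). Assumed: placebo response rates, size of the residual effect, within-patient correlations, and a common SD. The plan gives no figure for the residual effect, so there is none to reproduce. The sample size of 80 is used only as an input.

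**1. What each contrast contains.** Let T be the treatment effect, R the residual effect in group A during phase 2, and p1 and p2 the placebo, practice and period effects common to both groups.

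- Group A: phase 1 = p1 + T; phase 2 = p2 + R.
- Group B: phase 1 = p1; phase 2 = p2 + T.
- Phase 1 contrast (A − B) = T.
- Phase 2 contrast (B − A) = T − R.
- Phase 1 contrast − phase 2 contrast = R, provided T is the same in both phases.
- Active minus placebo within patient: A gives T − R + p1 − p2 and B gives T + p2 − p1, so the average is T − R/2.

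A placebo effect common to both groups cancels in the phase 2 contrast. What mixes there is residual with treatment effect. Residual, placebo and practice effects mix in group A's phase 2 result taken alone (p2 + R).

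**2. Illustration with 30% responding on active drug (assumed placebo rates and residuals).**

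| Placebo rate | Residual | Phase 1 contrast | Group A rate in phase 2 | Phase 2 contrast | Phase 1 − phase 2 |
|---|---|---|---|---|---|
| 20% | 0 | 10 | 20% | 10 | 0 |
| 10% | 10 | 20 | 20% | 10 | 10 |
| 5% | 15 | 25 | 20% | 10 | 15 |

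Phase 2 alone gives the same result in all three cases. The two phases together tell them apart.

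**3. Precision on one continuous scale, 40 per group.** Detectable difference at 80% power = (1.96 + 0.84) × SE, in SD units.

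- Assessment 6, A v B, unadjusted: 2.80 × √(2/40) = 0.63 SD.
- Phase 1 − phase 2, unadjusted, within-patient correlation r: 2.80 × √(4(1 + r)/40). This is 0.89 SD at r = 0, 1.09 at 0.5 and 1.22 at 0.9.
- Assessment 6 adjusted for baseline, correlation r with baseline: 2.80 × √(2(1 − r²)/40). This is 0.54 SD at r = 0.5, 0.45 at 0.7 and 0.27 at 0.9.
- Baseline adjustment helps the phase difference too. If all correlations equal r, the adjusted figure is 2.80 × √(2[2(1 + r) − 4r²]/40): 0.89 SD at r = 0.5, 0.75 at 0.7 and 0.47 at 0.9.

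Like for like, Assessment 6 is about 1.4 to 1.9 times as sensitive unadjusted (0.89/0.63 to 1.22/0.63) and about 1.6 to 1.7 times adjusted (0.89/0.54 to 0.47/0.27).

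**4. Responder scale, residual of 10 points (20% v 10%).**

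- Assessment 6: SE = √((0.16 + 0.09)/40) = 7.9 points, power about 24%.
- Phase difference, no correlation: SE = √((0.21 + 0.16 + 0.09 + 0.21)/40) = 12.9 points, power about 12%. At correlation 0.5, power is about 9%.

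**5. Week 22 taken literally.** Group B stopped fampridine at week 20, so it is 22 − 20 = 2 weeks off. Group A stopped at week 10, so it is 22 − 10 = 12 weeks off. That contrast is not the one the sentence asks for.

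**The case against.** The strongest reply is that the plan makes two comparisons. Phase 1 supplies a placebo rate that fampridine cannot have touched (group B), and setting it beside phase 2 is the natural reason for repeating the comparison. This stands. A reader might infer that the design cannot distinguish a residual effect from a placebo effect, or that the result would be uninterpretable. The documents do not support that: the residual is estimable from the two phases together. What remains is that the step is not stated, assumes no treatment-by-period interaction and is imprecise.

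A reader might also infer that the analysis is definitely set at a visit when everyone is off treatment. The sentence speaks of patients receiving active drug or placebo and refers to treatment phase 2, which fits week 20. The week 22 reading comes from a column label and from an administrative definition of trial end. This is a conflict of wording, not a proven mistiming.

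Assessment 6 has limits as well. It shows a residual effect at week 12 only, not at weeks 16 to 20, and its power is modest on the responder scale. Setting a detectable responder-rate difference from the phases beside a detectable percentage change at Assessment 6 would suggest a gain of several fold, but those are different units.

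Finally, the paragraph sits under the secondary endpoints, and the primary responder definition does not depend on it.

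**Conclusion.** The point holds in a limited form. The plan must reconcile its end-of-trial wording with its schedule. Its phase 2 comparison gives the treatment effect less any residual effect, and the plan does not say how the two phases will be combined to recover the residual. Assessment 6 offers a more direct randomised comparison from data already collected: about 0.63 SD detectable, against about 0.9 to 1.2 SD for the phase difference, unadjusted.

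These figures assume 40 evaluable patients per group, a common SD, correlations from 0 to 0.9, a two-sided 5% level, and Assessment 6 measurements taken before the first phase 2 dose. Loss to follow-up would make both methods less precise. Nothing here shows that a residual effect exists or that the primary analysis is invalid. This is a worthwhile improvement at almost no cost.

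**What to change.** In sections 9.4, 10.3.2 and 13.5:

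1. Replace the end-of-trial timing of the second active-v-placebo comparison with the end of treatment phase 2, naming Assessments 7 and 8. These are the phase 2 visits that the responder definitions already use.
2. Add a descriptive estimate of the residual effect at week 12: the group A minus group B difference in percentage change from baseline in 9-HPT and JTT at Assessment 6, adjusted for baseline (Assessments 1 to 3), with a 95% CI. State that it will be read alongside the two phase comparisons, that their difference estimates the residual only if the treatment effect is the same in both phases, and that it does not gate the primary analysis.

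The cost is a few lines of wording and one extra table. No new visit, measurement or patient is needed.

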10.3.2 Efficacy Assessment

A responder to study medication will be a subject who has a 20% improvement in the 9-HPT at both on treatment visits (assessment 4 & 5 or 7 & 8) compared with baseline visits.

A secondary measure of upper limb responsiveness will be defined as a 20% improvement in from baseline in the average time taken to complete all seven tasks on the JTT “on treatment” (assessments 4 & 5 or 7 & 8) compared with baseline assessments (assessments 1,2 & 3).

A mobility responder to fampridine will be defined as a patient with both of the two “on treatment” T25FW assessments (assessments 4 & 5 or 7 & 8) being better than the maximum of any of the four “off treatment” assessments (assessments 1, 2, 3, & 9). Otherwise the patient will be deemed a non-responder.

The responders to the 9-HPT and/or JTT will be compared to the non-responders in relation to their changes in the DASH and AMSQ on treatment and off treatment at the baseline assessment. The change in the DASH and AMSQ in responders at Assessment 5 or 8 (week 10 or 20) will be compared to non-responders at that time-point.

Upper limb response will be examined at the end of treatment phase 1 and repeated at the end of the trial by comparing patients receiving active drug with those receiving placebo to assess any placebo effect and allow assessment of any residual beneficial effect on those who receive fampridine in treatment phase 1 and then switch to placebo in treatment phase 2. Response will again be considered as a 20% improvement in the 9HPT in the active treatment group compared with placebo and a 20% improvement from baseline in the time taken to complete all seven tasks in the JTT. See earlier comment

The responders to the T25FW will be compared to the non-responders in relation to their changes in the MSWS-12 on treatment and off treatment at the baseline assessment. The change in the MSWS-12 in responders at Assessment 5 or 8 (week 10 or 20) will be compared to non-responders at that time-point.

The patients’ scores on the MSIS-29 (physical) and SF-36 will be examined in relation to the objective changes (responder/non-responder) in the 9-HPT, JTT and the T25FW

Safety Assessment

Adverse events will be monitored, through out the study. Subjects will be required to inform the study team of all new or worsening symptoms within 24 hours of onset. All adverse events will be recorded in the CRF.

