13.0 STATISTICS

13.1 DESCRIPTION OF STATISTICAL METHODS

Outcome will be assessed using the Wilcoxon Signed Rank test to establish whether there is a difference between the paired 'on treatment' outcome measures for each individual.

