13.2 DETERMINATION OF SAMPLE SIZE SUBJECTS

Given the previous reports, one would anticipate in this observational study that approximately 30+ % of patients would experience a significant (25%) improvement in indices of upper limb and walking mobility. Using a crossover design and treating the observations as paired within individuals, and allowing for loss to follow up during the trial, a sample size of 80 (40 in each arm) will be used.

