13.7 THE LEVEL OF STATISTICAL SIGNIFICANCE

A significance level of 0.05 will be used for all analyses.

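### The end-of-phase-1 fampridine-versus-placebo comparison of the 9-HPT is scored only by a 20% threshold; a baseline-adjusted analysis of log time should be added beside the responder counts

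*Combined protocol and SAP*

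**What the plan says.** Sections 9.4, 10.3.2 and 13.5 carry the same text. "Upper limb response will be examined at the end of treatment phase 1 and repeated at the end of the trial", with patients on active drug compared with those on placebo. The stated purposes are to gauge any placebo effect and any benefit that persists after switching to placebo. For the 9-HPT the scoring rule is: "Response will again be considered as a 20% improvement in the 9HPT in the active treatment group compared with placebo". The JTT half of that sentence refers to baseline; the 9-HPT half names only placebo.

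The responder definition earlier in section 13.5 requires both on-treatment 9-HPT times to be "improving 20% from the average of the baseline assessments (1, 2 & 3"). The only general test is in section 13.1: "Outcome will be assessed using the Wilcoxon Signed Rank test to establish whether there is a difference between the paired" on-treatment values within each person. Section 13.7 adds: "A significance level of 0.05 will be used for all analyses".

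On size, section 13.2 says "a sample size of 80 (40 in each arm) will be used" and expects that "approximately 30+ % of patients would experience a significant (25%) improvement in indices of upper limb and walking mobility". It gives no power, SD, correlation or placebo response rate. Section 10.3 and the schedule of events show the 9-HPT measured three times before treatment (Assessments 1-3) and twice in phase 1 (Assessments 4 and 5).

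**The concern.** At the end of phase 1 each patient has received one treatment only, so the comparison is parallel, about 40 against 40. A within-patient signed-rank test does not apply, and nothing else is specified. Under the responder reading, a timed measure is reduced to yes or no. Under a raw group-time reading, the wide spread between patients (entry range 15-90 s) stays in the error term. Neither reading uses baseline as a covariate, although three pre-treatment values exist for each patient.

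Phase 1 is the one active-placebo comparison that carry-over cannot affect, so it is the natural check on the crossover result. If it is insensitive, a non-significant result could be misread as absence of a drug effect. The plan also yields no estimate of the phase 1 treatment effect with a confidence interval.

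**Working it through.** **The plan's own figure.** No power is stated for this comparison, and the sample size of 80 cannot be reproduced without a placebo rate, a power and a dropout rate. For orientation, 30% against 6% responders needs 80 in total for 80% power with no dropout. At 40 per arm, 30% against 5%, 10%, 15% and 20% gives 85%, 61%, 36% and 17.5%.

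**Inputs from the documents.** 40 per arm; alpha 0.05 (two-sided assumed); three baseline and two on-treatment visits; responder = both on-treatment times at or below 0.80 of the baseline mean; about 30% of patients improving by 25%.

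**Assumed inputs.** Between-patient SD of log time 0.45 (15-90 s taken as four SDs: ln(90/15)/4 = 0.448). Visit CV v of 6-15%. Patient-by-phase SD p of 0-0.10.

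**Two readings of 25%.** Section 8.2 reports a 25% gain in walking speed; for a timed test that is 1/1.25 = 0.80, a 20% time cut, exactly on the threshold. Section 13.2 does not say speed or time, so a 25% time cut is equally open. A 10% time cut in all patients is added as a third case.

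**ANCOVA by hand.** Let a fraction f of patients have a time cut c. The effect is D = f × |ln(1−c)|. With the baseline slope close to 1, SE² = [2(5v²/6 + p²) + f(1−f)(ln(1−c))²]/40, and power is about Φ(D/SE − 1.96).

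- f = 0.3, c = 20%: D = 0.3 × 0.2231 = 0.0669.
  - v = 0.06, p = 0: SE² = (0.0060 + 0.0105)/40, SE = 0.0203, power Φ(1.34) = 91%.
  - v = 0.15, p = 0.10: SE² = (0.0575 + 0.0105)/40, SE = 0.0412, power Φ(−0.34) = 37%.
- f = 0.3, c = 25%: D = 0.0863. SE runs from 0.0242 to 0.0433; power 95% to 51%.
- f = 1, c = 10%: D = 0.1054. SE runs from 0.0122 to 0.0379; power about 100% to 79%.

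**Unadjusted log times.** SE is about 0.45 × √(2/40) = 0.101, so power is about 10%, 14% and 18% in the three cases.

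**Simulation of the full rules, 40 per arm:**

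| True effect | Responder rule, Fisher | Responder rule, chi-square | ANCOVA | Unadjusted log time |
|---|---|---|---|---|
| 30% of patients, 20% time cut | 14-27% | 30-57% | 36-91% | 9-20% across all three rows |
| 30% of patients, 25% time cut | 32-87% | 50-98% | 51-95% | |
| All patients, 10% time cut | 0-15% | 0-39% | 76-100% | |

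The simulated ANCOVA ranges agree closely with the hand calculation. ANCOVA type I error was 4.3-5.5%.

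**Why Fisher and chi-square differ.** At a 20% time cut without patient-by-phase variation, only 9-11% of fampridine patients are observed responders against 0-2% on placebo, or about 4 of 40 against 0 or 1. For 4 against 0, chi-square is 80 × (4 × 40)²/(40 × 40 × 4 × 76) = 4.21, which exceeds 3.84. The two-sided Fisher p is 2 × C(40,4)/C(80,4) = 0.116. Fisher needs 6 against 0 (p = 0.026), because 5 against 0 gives 0.055.

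**Sensitivity.** A separate run used between-patient SD 0.40, visit SD 0.08-0.15 and patient-by-phase SD 0.05-0.20, with 30% of patients having a 25% time cut. It gave Fisher 22-71%, chi-square 30-93% and ANCOVA 36-85%. At 36 per arm (10% loss) the values are a few points lower and the pattern is the same.

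**The case against.** The strongest objection concerns the size of the gain. One can pick a cell with about 15% power for the responder rule and 50-90% for ANCOVA, but that cell needs three choices the plan does not make:

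- **Fisher's test.** No test is named, and chi-square on the same counts gives 38-50% in that cell.
- **A 25% improvement read as speed.** Section 13.2 does not say so. At a 25% time cut the responder rule with chi-square equals or beats ANCOVA over most of the range.
- **No patient-by-phase variation.** With an SD of 0.10 and a 20% time cut, chi-square and ANCOVA are nearly equal.

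All of this stands, and power can be shown only as a range.

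It is also fair that baseline may not be ignored. The word *again* in the scoring sentence can carry over the earlier definition, which refers each patient to the mean of Assessments 1-3. A reader might infer that the plan makes no use of the baselines; the documents do not support that. They support only that baseline is not a covariate.

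Last, this is a secondary look in a crossover trial that has its own paired analysis, and no power is claimed for it. That limits the weight of the point but does not supply the missing analysis, because the paired test cannot be run on phase 1 alone.

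**Conclusion.** The point holds as a gap in a secondary analysis. The phase 1 comparison has no applicable test, discards the size of the change and uses no baseline covariate. Adjustment helps most when the benefit is a modest shift in all patients (76-100% against at most 39%). It usually helps when 30% of patients have a 20% time cut. It helps little, or loses to chi-square, when 30% have a 25% time cut. An unadjusted comparison of log times is weak throughout (9-20%).

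A reader might infer that the comparison would most likely be negative even if the drug works as section 13.2 expects. The documents do not support that: with 30% of patients at a 25% time cut, the responder rule has 32-98% power depending on test and variability. Every power figure rests on the assumed SDs and on 40 per arm with no loss.

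**What to change.** In section 13.5, mirrored in 9.4 and 10.3.2:

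- State that the 9-HPT responder rule in the phase comparison is referred to the mean of Assessments 1-3, if that is what is meant, and name the test for the responder counts.
- Add for phase 1 a comparison of log 9-HPT (mean of Assessments 4 and 5) between fampridine and placebo by ANCOVA, with log mean baseline (Assessments 1-3) as covariate and robust standard errors. Report the geometric mean ratio with 95% CI.
- Do the same for JTT time.
- Keep the 20% responder counts by arm alongside.
- If power is quoted, give a range with the assumed SDs, visit variability and test.

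The cost is one paragraph and one extra model per measure, with no new data or visits. The downside is that the responder count can be more powerful, by up to about 17 points with chi-square, when benefit is confined to a minority with large gains. That is why it stays.

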8.2 RATIONALE FOR THE STUDY

Treatment with fampridine (4-aminopyridine), a potassium channel blocker,^{1,2} has been shown to cause significant improvement in walking speed in one third of MS patients with motor disability.³⁻⁵ In those patients who respond, approximately a 25% improvement in walking speed was obtained with a self-reported 7 point improvement in the Multiple Sclerosis Walking Scale (MSWS-12), a patient-rated measure of walking quality and ability,^{6,7} in comparison to non-responding patients and placebo control subjects.

Pharmacologically, the K⁺ channel blocking properties of fampridine and its effects on action potential conduction in demyelinated nerve fiber preparations have been extensively characterized. At low concentrations that are relevant to clinical experience (in the range of 0.2 to 2 µM [18 to 180 ng/mL]), fampridine is able to block certain voltage-dependent K⁺ channels in neurons. It is this characteristic that appears to explain the ability of the drug to restore conduction of action potentials in some critically demyelinated nerve fibers. At higher (millimolar) concentrations, fampridine affects other types of K⁺ channels in both neural and non-neural tissues. Blockade of repolarising K⁺ currents may increase synaptic transmission throughout the nervous system by increasing the duration of the presynaptic action potential. A range of neurological effects consistent with increased excitability of nerve cells occurs with clinically relevant doses of fampridine.

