9.4 PRIMARY AND SECONDARY/ EXPLORATORY ENDPOINTS/OUTCOME MEASURES

Primary endpoint:

The primary end point will be identifying an upper limb responder to fampridine defined as a patient with both of the two “on treatment” 9-HPT assessments (assessments 4 & 5 or 7 & 8) improving 20% from the average of the baseline assessments (1, 2 & 3).

Secondary endpoints:

A secondary measure of upper limb responsiveness will be defined as a 20% improvement in from baseline in the average time taken to complete all seven tasks on the JTT “on treatment” (assessments 4 & 5 or 7 & 8) compared with baseline assessments (assessments 1,2 & 3).

A mobility responder to Fampridine will be defined as a patient with both of the two “on treatment” T25FW assessments (assessments 4 & 5 or 7 & 8) being better than the maximum of any of the four “off treatment” assessments (assessments 1, 2, 3, & 9). Otherwise the patient will be deemed a non-responder.

The responders to the 9-HPT and/or JTT will be compared to the non-responders in relation to their changes in the DASH and AMSQ on treatment and off treatment at the baseline assessment. The change in the DASH and AMSQ in responders at Assessment 5 or 8 (week 10 or 20) will be compared to non-responders at that time-point.

Upper limb response will be examined at the end of treatment phase 1 and repeated at the end of the trial by comparing patients receiving active drug with those receiving placebo to assess any placebo effect and allow assessment of any residual beneficial effect on those who receive fampridine in treatment phase 1 and then switch to placebo in treatment phase 2. Response will again be considered as a 20% improvement in the 9HPT in the active treatment group compared with placebo and a 20% improvement from baseline in the time taken to complete all seven tasks in the JTT. See earlier comment

The responders to the T25FW will be compared to the non-responders in relation to their changes in the MSWS-12 on treatment and off treatment at the baseline assessment. The change in the MSWS-12 in responders at Assessment 5 or 8 (week 10 or 20) will be compared to non-responders at that time-point.

The patients’ scores on the MSIS-29 (physical) and SF-36 will be examined in relation to the objective changes (responder/non-responder) in the 9-HPT, JTT and the T25FW.

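### The secondary phase comparison words the 9-HPT response criterion inconsistently with the primary responder rule; read literally, it asks for a 20% group gain where section 13.2 implies about 7.5%

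*Combined protocol and SAP*

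**What the plan says.** Sections 9.4, 10.3.2 and 13.5 define an upper limb responder at patient level, as someone whose 9-HPT improves by 20% over baseline at both on-treatment visits (4 and 5, or 7 and 8). Sections 9.4 and 13.5 spell out the reference as "improving 20% from the average of the baseline assessments (1, 2 & 3").

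The same three sections then describe a secondary look at upper limb response at the end of phase 1 and again at the end of the trial, "by comparing patients receiving active drug with those receiving placebo to assess any placebo effect" and to look for residual benefit in those who switch from fampridine to placebo. For this comparison: "Response will again be considered as a 20% improvement in the 9HPT in the active treatment group compared with placebo". The sentence goes on to give the JTT criterion as "a 20% improvement from baseline in the time taken to complete all seven tasks in the JTT". In all three places the paragraph ends with a leftover drafting note pointing to some earlier comment.

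Section 13.2 gives the planning assumption, "approximately 30+ % of patients would experience a significant (25%) improvement in indices of upper limb and walking mobility", and the size, "a sample size of 80 (40 in each arm) will be used". Section 8.2 shows where the 25% comes from: "In those patients who respond, approximately a 25% improvement in walking speed was obtained". It is a figure for responders, and for walking.

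**The concern.** The word *again* signals that the earlier rule is being reused, but the rule that follows differs from it. An analyst could follow either the patient-level rule or the literal sentence, and the two can lead to opposite conclusions from the same data. A 20% cut is reasonable for labelling one patient when some patients respond well and most do not. As a bar for the difference between two groups it is far higher, because non-responders dilute the group average. The stake is how the phase 1 and end-of-trial comparisons of active with placebo are reported. They are secondary, but they are where section 13.5 sets the two treatments against each other.

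**Working it through.** **1. The two rules side by side (9-HPT)**

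| Element | Primary endpoint | Phase comparison, as worded |
|---|---|---|
| Comparator | Patient's own mean of assessments 1, 2 and 3 | Placebo |
| Unit | Patient | Treatment group (literal reading) |
| Assessments | Both on-treatment visits | Not stated |
| JTT, for comparison | Own baseline | Own baseline |

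At the end of phase 1 each patient has received only one treatment. A gain over placebo cannot be computed within a patient at that point, so the literal wording can only describe a between-group quantity.

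**2. The plan's own figure.** The total of 80 cannot be reproduced. Section 13.2 states no power, placebo response, standard deviation or dropout rate. It is used below only for the group size of 40.

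**3. Group gain implied by section 13.2.** Inputs: responder share 30% and gain in responders 25% (13.2); one third as the alternative share (8.2). Assumption: no change in non-responders or on placebo, on which the plan is silent.

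Expected group gain = share x gain:
- 0.30 x 25% = 7.5%
- 1/3 x 25% = 8.3%
- 0.40 x 25% = 10%; 0.50 x 25% = 12.5%

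To reach 20% on average, one of these would be needed:
- 20/25 = 80% of patients gaining 25%
- 30% of patients gaining 20/0.30 = 66.7%
- non-responders gaining (20 - 7.5)/0.70 = 17.9%

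**4. Chance of observing 20 points or more anyway.** Let SD be the standard deviation of percentage change apart from the responder mixture. The plan gives none, so 10 to 30 points is assumed. The mixture adds 0.30 x 0.70 x 25² = 131.25 to the variance in the active group. With n per group:

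SE = √[(SD² + 131.25)/n + SD²/n], and P = 1 - Φ[(20 - 7.5)/SE]

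| SD | n = 40 | n = 32 (20% loss, assumed) |
|---|---|---|
| 10 | 0.001% | 0.005% |
| 15 | 0.05% | 0.17% |
| 20 | 0.5% | 1.0% |
| 25 | 1.7% | 2.9% |
| 30 | 3.6% | 5.4% |

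If the criterion is instead a ratio of raw 9-HPT times, baseline imbalance adds noise. A simulation of 20,000 trials with 40 per group, baselines assumed uniform on 15 to 90 seconds and within-patient variation of 10% or 20%, gave about 7% to 9% for a ratio of means and about 21% for a ratio of medians.

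**5. The patient-level reading.** Take 30% responders on fampridine, 40 per group and a two-sided 0.05 test of two proportions (normal approximation). Power is about 98%, 85%, 61% and 36% for placebo response of 0, 5, 10 and 15% (assumed values). The 7.5% versus 20% problem does not arise here.

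**The case against.** The group reading is not the only one. The paragraph opens by comparing patients on the two treatments, says *again*, and keeps own baseline for the JTT. All of this fits the primary patient-level rule applied in each arm, with the arms then compared. No section mentions a group mean. Even a 20-point difference in responder proportions, another possible meaning, would be expected if placebo response is 10% or less. This stands: the group reading is the literal one, but not certain. It does not remove the inconsistency, since it requires setting aside the words that make placebo the comparator.

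Three stronger inferences are tempting, and the documents do not support them:

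- *That the 20% bar could never be met.* Section 13.2 allows more than 30% responding and is silent on change in non-responders and on placebo, and sampling error leaves the small chances shown above. The supportable statement is that the bar would not be expected to be met.
- *That an effective drug would be declared a failure.* The paragraph is a secondary assessment of placebo and residual effects, with no decision rule attached. The primary endpoint keeps its patient-level definition.
- *That this is the plan's only contrast of active with placebo.* Within 13.5 it is the only explicit one, but the paired Wilcoxon signed rank test in 13.1 is plausibly another, although tersely described.

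**Conclusion.** The criterion is inconsistently worded in all three sections and should be corrected. It departs from the primary rule in comparator, in unit on the literal reading, and in the number of assessments required. It also departs from the JTT half of its own sentence. None of this depends on a numerical assumption.

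The size depends on the reading. On the literal group reading, with no change in non-responders or on placebo, the expected gain is 7.5% to 8.3% against a bar of 20%, well under half. For mean percentage change with 30% responding, the chance of reaching the bar is about 0.001% to 3.6% at 40 per group for assumed SDs of 10 to 30. It is larger if more patients respond or if raw times are compared. On the patient-level reading there is no such shortfall. The effect is confined to a secondary comparison.

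**What to change.** In 9.4, 10.3.2 and 13.5, replace the sentence with text along these lines: *In each treatment period a patient is a 9-HPT responder if both on-treatment assessments in that period improve by at least 20% on the patient's own mean of assessments 1, 2 and 3; JTT response is defined as in 13.5 a). Responder proportions will be compared between fampridine and placebo in phase 1, and within patients across the two periods, each as a difference with a 95% confidence interval. Any mean difference in 9-HPT will be reported separately, without a 20% threshold.* Delete the leftover drafting note in all three places.

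The within-patient comparison matches the pairing that 13.2 relies on. The paragraph's other purpose, residual benefit after switching to placebo, is not settled by this wording and needs its own stated contrast.

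The cost is a wording amendment to protocol and statistics sections. Because it changes endpoint text, it goes to the ethics committee under section 19.0, and section 19.3 applies if it is classed as substantial. It needs no new data, visits or patients.
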